5.0 Number of Subjects

LOCAL:

5.1 We expect to consent, enroll, and randomize a total of 54 CCGs.

5.2 The sample size was based on practical/budgetary constraints as well as a preliminary power analysis. A power analysis was conducted to determine the minimum sample

FULL PROTOCOL TITLE: CARING FOR CAREGIVERS WITH MIND-BODY EXERCISE

size that is required to find significance with a power set of .80, an alpha level at .05, correlation among the repeated measures of 0.3, and a moderate effect size of .25 using G*Power version 3.1. Based on the primary analysis, to ensure sufficient power on the repeated measure ANOVA (3 time points x 3 groups), a total of 48 participants are required. In consideration of 10-15% of attrition rate, a total of 54 participants will be recruited.

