7.0 Study Timelines

7.1 For Cohorts 1 and 2, we will randomize (1:1:1) 24 CCGs to one of three conditions: (1) A community- based Qigong program; (2) an internet-based Qigong program; or (3) a self-care control group. For Cohort 3, we will randomize (2:1) 15 CCGs to one of two conditions: (1) an internet-based Qigong Program, or (2) a self-care control group. For Cohort 4, we will randomize (2:1) 15 CCGs to one of two conditions: (1) a community-based Qigong program, or (2) a self-care control group. Our primary outcomes are feasibility and acceptability.

7.2 Participants in the community-based programs will attend one, 75 minutes class per week supplemented by home practice (guided by printed materials) for 20 minutes on 3 additional days. Participants in the internet-guided program will be asked to follow two online sessions for 40 minutes each, also supplemented by home practice for 20 minutes on 3 additional days. Participants in both Qigong groups will commence training within 2 weeks of baseline visits. Caregivers randomized to either Qigong intervention can expect a total time commitment of 30 hours to complete all study related activities.

Individuals randomized to the self-care control group will be provided with an educational book on caregiving, they will also be provided with a “Self-Care Manual” that includes self-guided activities related to caregiving and caregiver health. Caregivers randomized to this group can expect about a 5-hour total time commitment to study related activities.

7.3 Baseline and 12-week assessments including psychosocial measures and QOL, physical function and cognitive measures will occur in person for all participants at the University of Houston College of Nursing in Sugarland, [name]. In addition, a short qualitative interview will be conducted with participants in the community-based and internet-based classes. A longer-term 6-month follow-up will assess psychosocial and QOL measures using a mail-in questionnaire packet. Primary analyses should be complete by 08/31/2021.

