9.1 Procedures Involved

9.1 Using CCGs as a representative population of the larger CG population, our long-term goal is to conduct a large-scale fully powered trial evaluating a widely accessible and previously studied Qigong regimen (Eight Brocades, Baduanjin

FULL PROTOCOL TITLE: CARING FOR CAREGIVERS WITH MIND-BODY EXERCISE

Qigong). Interventions will be delivered either in community-based groups led by instructors or via internet to individuals learning thru recorded guided instruction

FULL PROTOCOL TITLE: CARING FOR CAREGIVERS WITH MIND-BODY EXERCISE

supplemented with intermittent virtual live feedback from instructors. Outcomes will include QOL, fatigue, sleep disturbances, psychological distress, CG burden, and physical function. The short-term goals of this R34 are to conduct a mixed-methods pilot randomized controlled trial (RCT) to inform the feasibility and design of a definitive trial. We will address these goals by randomizing 54 CCGs to one of three conditions: (1) A community-based Qigong program; (2) an internet-based Qigong program; or (3) a self-care control group.

9.2 At the baseline visit, eligibility will be confirmed, consent will be obtained, and the consent process will be documented. Written informed consent will be obtained by the research assistant or study staff. The subject will be asked to review the study consent form. Investigator or research staff will meet with the subject to review the form, to confirm the subject's understanding of the study, and to answer any questions that the subject might have. Once the subject demonstrates understanding of the study and agrees to participate in the study, the consent will be signed in the presence of the investigator or research staff. Informed consent will be obtained and reviewed by the University of Houston Institutional Review Board as appropriate. For the duration of the Covid-19 Pandemic, all participants and research staff will follow the University of Houston Department of Research's Covid-19 precautions. These precautions will be followed during any in-person assessment or in-person Qigong class. All participants and research staff will have a contactless temperature screening prior to any in-person activity. Masks will be worn and social distancing maintained during all in-person assessments and in-person Qigong classes.

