Estimating variance for future power calculations. We will use linear mixed models with fixed effects of visit and treatment x post-baseline visit interaction and unstructured covariance among repeated measures to analyze efficacy outcomes. This will yield six variance components required for future power calculations. The Wald statistic from the treatment x visit interaction testing 12-week treatment-dependent response will be used to estimate the effect of Qigong and as a criterion for selecting outcomes that are potentially sensitive to Qigong. Selection of the outcomes to include in our future trial, and which to select as the primary outcome, will also be

FULL PROTOCOL TITLE: CARING FOR CAREGIVERS WITH MIND-BODY EXERCISE

guided by consideration of clinical relevance, participant burden, and cost. The study will have 80% power to identify the outcome that is truly most responsive to Qigong from among the 14 measures calculated from the 12 assessments completed at 12 weeks if the most responsive measure is associated with an effect size at least 0.43 SD greater than the others.

Inter-rater reliability and validity testing of proficiency instrument. Inter-rater reliability will be evaluated using Cohen's Kappa statistic. Validity testing based on cross-sectional comparisons of proficiency scores and practitioner's years of training will utilize Pearson's correlations. Associations between longitudinal changes in proficiency and clinical outcomes will be evaluated using mixed model approaches described above.

Qualitative analysis. Semi-structured qualitative interviews will be audio recorded and transcribed verbatim. Thematic analysis will be informed by grounded theory methods to guide description of qualitative interviews. Questions will focus on facilitators/barriers to recruitment/participation, and acceptability of the intervention and its specific components. Two investigators will independently code transcripts to identify emergent themes in an iterative process until thematic saturation is reached as in prior studies.^{47, 48 49-51} Transcription, coding, and analysis will be conducted in NVivo v11.

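### The Wald statistic used to select outcomes has no stated contrast, degrees of freedom or direction; on the default three-arm reading it scores benefit and harm alike and can reward opposite effects of the two delivery modes

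*Combined protocol and SAP*

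**What the plan says.** Section 19.1 (19.0 Data Management, paragraph on estimating variance for future power calculations) plans "linear mixed models with fixed effects of visit and treatment x post-baseline visit interaction and unstructured covariance among repeated measures" for the efficacy outcomes. It continues: "The Wald statistic from the treatment x visit interaction testing 12-week treatment-dependent response will be used to estimate the effect of Qigong", and gives the same statistic a second use, "as a criterion for selecting outcomes that are potentially sensitive to Qigong". Clinical relevance, participant burden and cost are then named as further guides to the choice of outcomes and of the primary outcome. The paragraph closes with a claim of 80% power to pick out the most responsive of 14 measures when its effect exceeds the others by 0.43 SD.

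The paragraph does not say how treatment is coded, which contrast is tested, how many degrees of freedom the statistic has, or how direction enters. Elsewhere treatment has three levels: section 9.1 speaks of "randomizing 54 CCGs to one of three conditions", section 7.1 says of Cohorts 1 and 2 "we will randomize (1:1:1) 24 CCGs to one of three conditions", and section 5.2 is based on a "repeated measure ANOVA (3 time points x 3 groups), a total of 48 participants are required".

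**The concern.** A Wald statistic is a test quantity. It measures distance from no difference relative to sampling error, and in its usual chi-square or F form it has no sign. With a three-level treatment factor, the 12-week interaction is tested on 2 df. The statistic is then large when any two arms differ, including community versus internet, and whichever way they differ. That is not the same as sensitivity to Qigong compared with control.

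The pilot exists to inform the design of a definitive trial, and this is the only statistical criterion named for choosing that trial's outcomes. A poorly aimed criterion could put on the shortlist an outcome that Qigong worsens, or one with no average Qigong effect, ahead of one that both modes improve.

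**Working it through.** **1. The plan's own figures.** For a signed scalar effect, the chance that the best of 14 equally precise, independent estimates ranks first is P = ∫ φ(x) Φ(x + δ/se)^13 dx. P = 80% needs δ/se = 2.63, so se = 0.43/2.63 = 0.164 SD. With unit SD and independent outcomes:
- pooled Qigong v control (36 v 18): se = √(1/36 + 1/18) = 0.289, P = 44%
- one mode v control (18 v 18): se = √(2/18) = 0.333, P = 37%

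The stated 80% is reached if the outcomes correlate at about 0.68 (pooled) or 0.76 (one mode), among other combinations. The documents give none of these inputs, so the 80% is neither confirmed nor refuted. The sample size does reproduce: with "correlation among the repeated measures of 0.3, and a moderate effect size of .25 using G*Power version 3.1", the 3 x 3 interaction has power 0.81 at N = 48 (0.78 at 45). That calculation treats the arms as three groups.

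**2. Coding.** "This will yield six variance components required for future power calculations": an unstructured 3 x 3 covariance has 3 x 4/2 = 6 parameters. This fixes three visits and says nothing about treatment coding. No section pools the Qigong arms for efficacy, so three levels, and 2 df at 12 weeks, is the default reading. It is an inference.

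**3. Arm sizes (section 7.1).** Reading Cohorts 1 and 2 as 24 in total: 8/8/8. Cohort 3 adds 10 internet and 5 control; Cohort 4 adds 10 community and 5 control. Each arm has 18, total 54.

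**4. Noncentrality.** Assumptions: unit known SD, no dropout, control at 0, effects in SD units with positive as benefit. The 2-df noncentrality is 18 x Σ(μj - mean)². For the pooled contrast it is (average Qigong effect)²/(1/36 + 1/18).

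| Community, internet | 2-df | Pooled 1-df |
|---|---|---|
| +0.5, +0.5 | 3.0 | 3.0 |
| -0.5, -0.5 | 3.0 | 3.0 |
| +0.5, -0.5 | 9.0 | 0 |
| +0.5, 0 | 3.0 | 0.75 |
| +0.5, +0.25 | 2.25 | 1.69 |
| +0.25, -0.25 | 2.25 | 0 |

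Opposite effects of size a give 18 x 2a² = 36a². This exceeds 3.0 only when a > √(3/36) = 0.29 SD, a gap between modes of about 0.58 SD.

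**5. Two independent outcomes, one with +0.5 in both modes.** The 2-df statistic ranks a -0.5/-0.5 outcome above it 50% of the time and a +0.5/-0.5 outcome above it 80% of the time. With the signed pooled contrast these are 0.7% and 11%. A +0.25/-0.25 outcome is ranked above it 44% of the time by the 2-df statistic.

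**6. Fourteen outcomes.** Simulation, 200,000 replicates, with outcome correlation set at 0.68 so that the signed pooled contrast gives the plan's 80%. All other outcomes are at 0 unless stated.

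| Truth | 2-df | Unsigned 1-df | Signed pooled |
|---|---|---|---|
| Best +0.43, others 0: correct pick | 42% | 53% | 80% |
| Best +0.63, others +0.2: correct pick | 60% | 71% | 80% |
| Best +0.83, others +0.4: correct pick | 71% | 78% | 80% |
| One +0.43, one -0.43: picks improved / worsened | 36% / 36% | 42% / 42% | 81% / 0% |
| One +0.43 in both modes, one +0.4/-0.4: picks consistent / opposed | 19% / 63% | 53% / 4% | 80% / 2% |

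If the 80% is instead obtained with independent outcomes and a smaller standard error (equivalent to 56 per arm), the first row becomes 63%, 72% and 80%.

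**The case against.** **The degrees of freedom are not in the text.** A reader might infer that the plan specifies an unsigned 2-df test. It does not. The reference to the effect of Qigong and the single 0.43 SD gap suggest that one scalar was in mind, and a 1-df Wald statistic can be reported with its sign. The feasibility paragraph of 19.1 also shows that the planners compare each mode with control when they mean to. This stands as a limit on certainty. It does not remove the point, because no scalar is defined and an unsigned 1-df version still cannot tell benefit from harm.

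**The statistic is not the only criterion.** A reader might infer that a harmful outcome would be selected automatically. The documents do not support that: clinical relevance, burden and cost also count, and the fitted model gives signed coefficients that the investigators would see. The simulations in step 6 treat the statistic as the sole rule and so show its behaviour in isolation. Still, none of the other criteria is written as a check on direction or on consistency between modes.

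**The statistic does not generally prefer disagreement.** A reader might infer that any difference between modes is rewarded over consistent benefit. Step 4 shows otherwise: +0.5/0 ties with +0.5/+0.5, and both +0.5/+0.25 and +0.25/-0.25 score lower. The 80% needs two deliveries of the same regimen to act in opposite directions, 1.0 SD apart, and nothing in the documents makes that likely.

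**Scale direction is not a further fault.** Higher grip strength is better and a higher PHQ-9 score is worse, but reversing a scale leaves an unsigned statistic unchanged. Coding matters only once signed contrasts are used.

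**Pooling has its own cost.** Section 12.2 foresees a comparative effectiveness trial of both delivery methods. For an effect of 0.5 SD in one mode only, the pooled contrast has noncentrality 0.75 against 3.0 for the 2-df test, and power of only 0.14 at two-sided 5%. This stands and shapes the fix.

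**Conclusion.** The point holds as one about an undefined criterion whose default reading is not aimed at its stated purpose. Two parts need separating. The direction problem applies to any unsigned Wald statistic, on 1 or 2 df: equal benefit and harm score the same, at noncentrality 3.0 for 0.5 SD. The mode problem needs treatment as a three-level factor and opposite effects of more than about 0.29 SD each, when compared with a consistent 0.5 SD benefit.

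The practical loss depends on the truth. In the 14-outcome comparison at correlation 0.68, the 2-df statistic picks correctly 42% of the time against 80% for the signed pooled contrast when the other outcomes do not respond, but 71% against 80% when they all improve by 0.4 SD. These figures assume 18 per arm, unit known SD, no dropout and equal correlation between outcomes.

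The primary objectives (feasibility, learnability, delivery) do not depend on this, and no conclusion about Qigong in this trial rests on it. It should be changed because it feeds the choice of the next trial's outcomes and costs almost nothing to correct.

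**What to change.** In section 19.1, replace the interaction Wald statistic as the statistical selection criterion with signed, standardised 12-week Qigong-minus-control contrasts from the planned mixed model. Code every outcome so that positive means benefit, and report each contrast with its confidence interval:
- the two Qigong arms pooled v control
- community v control
- internet v control

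State that the mode-specific contrasts are weighed together with the pooled one, since the pooled contrast alone is insensitive to an effect confined to one mode. Keep the 2-df interaction test only as a secondary overall check, and use a community v internet contrast to show whether the modes differ. State which contrast, SD and outcome correlation lie behind the 0.43 SD and 80% figures.

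The cost is SAP wording, a few contrast statements in a model already planned, and slightly longer reporting. No new data are needed.

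### The stated 80% power to pick the most responsive of 14 measures at a 0.43 SD gap is unsupported by the inputs the protocol gives, and a Wald statistic is named as the effect estimate

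*Combined protocol and SAP*

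**What the plan says.** Section 19.1 of the combined protocol and SAP (Estimating variance for future power calculations) fits linear mixed models to the efficacy outcomes and then says: "The Wald statistic from the treatment x visit interaction testing 12-week treatment-dependent response will be used to estimate the effect of Qigong". The same statistic is a criterion for choosing outcomes for the future trial, and that choice is also "guided by consideration of clinical relevance, participant burden, and cost". The paragraph ends with the selection claim: "The study will have 80% power to identify the outcome that is truly most responsive to Qigong from among the 14 measures", provided the best measure has an "effect size at least 0.43 SD greater than the others".

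The only related inputs are elsewhere:

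- Section 5.2 uses a "correlation among the repeated measures of 0.3" for a repeated-measures ANOVA, concludes that "a total of 48 participants are required", and adds: "In consideration of 10-15% of attrition rate, a total of 54 participants will be recruited".
- Section 7.1 sets the allocation. For Cohorts 1 and 2, "we will randomize (1:1:1) 24 CCGs to one of three conditions". Cohorts 3 and 4 each randomise 15 caregivers 2:1 between one Qigong mode and control.

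**The concern.** The probability of picking the best of 14 noisy estimates depends on five things: the contrast, the SD that the gap is measured in, the number of completers, the correlation over time within an outcome, and the correlation between outcomes. Section 19.1 gives none of them, and the arms are small.

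The second problem is the statistic. A Wald statistic measures evidence against a null hypothesis and is not an estimate of how much Qigong changes an outcome. With three arms, the natural reading of a treatment by visit test at 12 weeks has 2 df and no sign. It could then favour an outcome that worsened, or one that differs only between the two delivery modes.

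The pilot is meant to inform the design of a definitive trial, including its primary outcome. Readers told 80% may trust the statistical ranking more than they should.

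**Working it through.** **Allocation (section 7.1).** The 24 in Cohorts 1 and 2 give 8/8/8. Cohort 3 gives 10 internet and 5 control. Cohort 4 gives 10 community and 5 control. The total is 24 + 15 + 15 = 54, or 18/18/18, so pooled Qigong v control is 36 v 18. With 48 completers at the same ratio it is 32 v 16.

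**Formula.** With 13 measures tied at a distance *gap* below the best and a common correlation r between outcomes, the probability of ranking the best first is

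P = ∫ φ(z) Φ(z + δ)^13 dz, with δ = gap / (SE × √(1 − r)).

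Ties are the least favourable case allowed by the plan's condition, so P is a minimum.

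**The plan's own figure.** P = 0.80 with 14 measures needs δ = 2.628. At a gap of 0.43 this means SE × √(1 − r) = 0.43 / 2.628 = 0.164. The documents give no inputs that produce this value, so the 80% cannot be reproduced from them.

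**Standard errors.** The model has no baseline treatment term, so in baseline-SD units SE ≈ √[(1/nQ + 1/nC)(1 − rho²)], where rho is the correlation between baseline and 12 weeks. Taking rho = 0.3 from section 5.2 is an assumption.

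- 36 v 18: √(0.08333 × 0.91) = 0.275
- 32 v 16: √(0.09375 × 0.91) = 0.292
- 36 v 18 on the SD-of-change scale, which needs no rho: √0.08333 = 0.289

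**Minimum probability at a gap of 0.43 SD** (δ in brackets):

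| Setting | r = 0 | r = 0.3 | r = 0.5 |
|---|---|---|---|
| 54 completers, rho = 0.3 | 47% (1.56) | 57% (1.87) | 68% (2.21) |
| 48 completers, rho = 0.3 | 44% (1.47) | 54% (1.76) | 64% (2.08) |
| 54 completers, SD of change | 44% (1.49) | 54% (1.78) | 65% (2.11) |

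**What would give 80%** (54 completers):

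- A larger gap at rho = 0.3: 2.628 × 0.275 × √(1 − r) = 0.72 / 0.61 / 0.51 SD for r = 0 / 0.3 / 0.5.
- A higher r at rho = 0.3: r = 1 − [0.43 / (2.628 × 0.275)]² ≈ 0.65.
- A higher rho: at rho = 0.6 and r = 0.5, SE = 0.289 × 0.8 = 0.231 and δ = 0.43 / (0.231 × 0.707) = 2.63, so P = 80.1%. With 48 completers, SE = 0.306 × 0.8 = 0.245, δ = 2.48 and P = 76%.

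**Form of the ranking statistic.** This was simulated with 200,000 draws, 18 per arm, rho = 0.3, the same effect in both modes, and the best measure 0.43 SD ahead. The table gives the percentage of trials in which the best measure ranks first, at r = 0 / 0.3 / 0.5.

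| Statistic | Other outcomes at 0.2 SD | Other outcomes null |
|---|---|---|
| Signed pooled contrast | 47 / 57 / 68 | 47 / 57 / 68 |
| Unsigned 1-df Wald | 46 / 54 / 62 | 35 / 39 / 46 |
| 2-df three-arm Wald | 41 / 46 / 53 | 28 / 31 / 37 |

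A signed 1-df Wald z with estimated variance is close to the signed estimate: 45.8% against 46.6% at r = 0 with the other outcomes null.

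**The case against.** The strongest reply is that rho = 0.3 belongs to a different calculation. A reader might infer that the 80% contradicts the protocol's own inputs. The documents do not support that, because section 5.2 states the 0.3 for the repeated-measures ANOVA and section 19.1 states no correlation at all. This stands, and it limits the finding to an unsupported figure. It does not rescue the 80%, since the SD-of-change scale needs no rho and gives 44 / 54 / 65%.

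A second reply is that several questionnaires overlap in content, so independent outcomes are a pessimistic case, and that real runners-up would not all be tied. Both points are fair. With the other 13 spread evenly over 0.2 SD below the runner-up (an arbitrary choice), 54 completers and rho = 0.3, the probabilities are 58 / 69 / 80%. But the plan's condition sets only a minimum gap, so what it can guarantee is the tied case. The r = 0.5 that is needed even in the milder case is also unstated.

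On the Wald statistic, a reader might infer that it is unfit for ranking in any form. That goes too far. A signed 1-df Wald z shows direction and orders outcomes almost as the standardised effect does. It also reflects precision gained from the baseline measurement, which matters for a later trial. The loss arises only with unsigned or 2-df forms, and section 19.1 does not state the degrees of freedom.

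Finally, the ranking is one consideration beside clinical relevance, burden and cost, and the primary outcomes are feasibility and acceptability. That limits the consequence.

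**Conclusion.** The concern holds in a limited form. For the contrast that section 19.1 names, the minimum probability of ranking the best measure first at 0.43 SD is 47 / 57 / 68% with 54 completers and 44 / 54 / 64% with 48, at r = 0 / 0.3 / 0.5. This rests on pooled Qigong v control, the borrowed rho = 0.3, tied competitors, equal correlation between outcomes, the same effect in both modes, known variances and dropout equal across arms. A reader might conclude that 80% is impossible, but higher correlations that the documents neither state nor exclude would reach it.

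Saying that a Wald statistic estimates the effect of Qigong is wrong as written. Whether the ranking itself suffers depends on a form that the plan does not specify.

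The problem is confined to the selection paragraph. The separate total of 48 in section 5.2 does reproduce (power 0.81 for the group by time interaction at f = 0.25 and correlation 0.3). The feasibility outcomes and the sample size are not affected.

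**What to change.** (a) Restate the selection claim as a minimum, with the sponsor's own inputs filled in. For example: if the other 13 measures are tied [gap] SD below the best, the probability of ranking the best measure first is at least [x]%, for the 12-week pooled Qigong v control contrast on the [baseline or change] SD scale, with [n] completers, correlation over time [rho] and correlation between outcomes [r]. Keep 80% at 0.43 SD only if those inputs give it. Otherwise lower the percentage or raise the gap.

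(b) Estimate the effect of Qigong by the 12-week pooled Qigong v control contrast from the mixed model, with its confidence interval. Rank outcomes by that signed 1-df contrast, with positive meaning benefit, and say whether the ranking uses its Wald z or the estimate divided by the baseline SD. Keep clinical relevance, burden and cost alongside it, and also report each delivery mode v control with its confidence interval.

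The cost is wording in the analysis plan, with no change to visits, sample size or the primary feasibility analysis. The downside is that the stated figure may become less favourable, and that differences between delivery modes are reported but do not drive the ranking.

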1.0 Objectives

1.1 Using cancer caregivers (CCGs) as a representative population of the larger CG population, our long-term goal is to conduct a large-scale fully powered trial evaluating a widely accessible and previously studied Qigong regimen (Eight Brocades, *Baduanjin Qigong*). The goal of this R34 is to conduct a mixed-methods pilot randomized controlled trial (RCT) to inform the feasibility and design of a future larger definitive trial.

Primary Objectives:

1. To finalize intervention content and delivery of both in-person community-based group and individual internet-based Qigong protocols.
2. To assess the 'learnability' of Qigong delivered in community-based group classes and via an internet-based protocol using a novel proficiency instrument.
3. To evaluate the feasibility of recruiting and retaining cancer caregivers into a 12-week clinical trial, and completing all outcomes testing protocols.

1.2 We hypothesize that participant recruitment, retention, and adherence to intervention and assessment protocols will comply with target goals. Feasibility will be assessed with respect to participant recruitment, retention, intervention adherence, and intervention acceptability. We will assess recruitment feasibility by the number of screened and eligible participants and the number refusing to participate. We will document reasons for refusal. This domain of feasibility will require: a) $\geq 50\%$ screened individuals are study eligible and b) $\geq 5-10\%$ of eligible participants are willing to consent. With a goal of $n = 54$ enrolled over a one-year period, we will need to screen 14 participants per month. Participant retention will be deemed feasible if loss to follow-up is $\leq 20\%$. Intervention adherence will require: a) $\geq 70\%$ participation in community or internet-guided classes and $> 50\%$ compliance with home practice guidelines. Qualitative interviews with CCGs, including those who drop out and have low adherence, will be used to further inform overall study feasibility, and facilitators and barriers to participation.

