At the initial visit at University of Houston, College of Nursing, participants will complete informed consent. This date will be recorded on a case report form as the date of enrollment into the study.

In addition, at this visit initial assessment related to QOL, psychological well-being, caregiver burden, cognitive and physical function will be measured. All outcomes will be assessed at baseline and 12 weeks, following completion of the 12-week intervention. All in-person assessments will be conducted by trained research assistants. Baseline and follow-up assessments are estimated to require 2.0 hours.

At the baseline and 12-week appointments, consented participants will be videotaped performing the Eight Brocades. This video will help assess learnability of the intervention and help with the development of the scoring instrument.

Semi-structured, open-ended interviews lasting approximately 30 minutes will be conducted at the 12-week assessment for participants in all groups. Questions will focus on characterizing participants' perceived effectiveness and enjoyability of the Qigong intervention, both community-based and internet-based, and identifying facilitators and barriers to participation. Questions specific to the mode of intervention delivery may include those related to use of technology, the role of face-to-face instructor feedback, perceived motivators to adherence, and self-efficacy.

In weeks 1, 2, 4 and 6 of the program, participants will participate in a one-to-one call with a Qigong instructor. This call will be audio recorded and will give participants

FULL PROTOCOL TITLE: CARING FOR CAREGIVERS WITH MIND-BODY EXERCISE

the opportunity to address any training- related questions or concerns, and to receive personalized feedback and encouragement from the instructor. At the 12-week assessment, participants will be asked to return the computer tablet. Participants will

FULL PROTOCOL TITLE: CARING FOR CAREGIVERS WITH MIND-BODY EXERCISE

be asked to keep track of their home Qigong practice on provided logs throughout the study. We will ask participants to send their logs to the study researchers at the end of each week, and we will provide them with stamped envelopes for mailing.

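### Cohen's kappa, with no weights and no stated unit, is the only inter-rater statistic for a proficiency measure that the plan then analyses as a quantitative score

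*Combined protocol and SAP*

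**What the plan says.** Section 1.1 makes learnability the second primary objective, to be assessed "using a novel proficiency instrument". Section 9.2 has participants filmed performing the Eight Brocades at baseline and 12 weeks and adds: "This video will help assess learnability of the intervention and help with the development of the scoring instrument".

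The analysis stands in section 19.1, in the paragraph on the proficiency instrument. Three sentences matter:

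- Reliability: "Inter-rater reliability will be evaluated using Cohen's Kappa statistic".
- Validity: "Validity testing based on cross-sectional comparisons of proficiency scores and practitioner's years of training will utilize Pearson's correlations".
- Change: "Associations between longitudinal changes in proficiency and clinical outcomes will be evaluated using mixed model approaches described above". The models referred to are introduced earlier in 19.1: "We will use linear mixed models with fixed effects of visit and treatment x post-baseline visit interaction".

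The documents do not give the range of the score, the item format, the number of raters, the number of videos to be rated, a weighting scheme for kappa, or a target for reliability. No ICC is named.

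**The concern.** Cohen's kappa without weights is a statistic for nominal categories. It asks only whether two raters gave the identical category, and a one-point difference counts the same as a difference across the whole scale. A Pearson correlation and an analysis of change, by contrast, use the distances between scores. What those analyses depend on is the reliability of the score as a quantity, and unweighted kappa does not estimate it.

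The instrument is new and a primary objective uses it, so its reliability is one of the things a reader will take from this pilot. A low kappa on a many-level score could make a sound instrument look poor when the definitive trial is designed. A kappa calculated on single items would say nothing direct about the score that enters the correlations and the change analyses.

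**Working it through.** The plan gives no reliability figure, so there is nothing of its own to reproduce. The check asks how far unweighted kappa departs from measures that credit near-agreement when rater quality is held fixed.

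**Inputs.** From the documents: kappa is the only statistic (19.1), and at most 54 participants can be rated per visit (5.1). Assumed, because the documents are silent: two raters, no systematic difference between them, normal true scores, a true ICC of 0.80 or 0.90, and 2 to 25 score levels.

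**Formulas.** With p_o the observed and p_e the chance proportion of exact agreement,

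- unweighted kappa = (p_o − p_e) / (1 − p_e);
- quadratic-weighted kappa = 1 − Σ(i−j)²·O_ij / Σ(i−j)²·E_ij, where O and E are the observed and chance-expected proportions for levels i and j.

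**Two levels, exact result.** For a cut at the mean, kappa = (2/π)·arcsin(ICC) = (2/π)·arcsin(0.90) = 0.71. Weighting changes nothing, because the only possible disagreement is one level.

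**Five equal-width levels over ±2.5 SD, true ICC 0.90.** The cuts at ±0.5 and ±1.5 SD give level probabilities 0.067, 0.242, 0.383, 0.242 and 0.067, so p_e = 2(0.067²) + 2(0.242²) + 0.383² ≈ 0.272. Simulation gives p_o = 0.660. Kappa = (0.660 − 0.272)/(1 − 0.272) = 0.388/0.728 = 0.53. Yet 99.6% of pairs are within one level, and quadratic-weighted kappa on the same ratings is 0.83.

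**Across the number of levels.** Results come from simulated rating pairs (400,000 or more per setting). Ranges cover equal-width and equal-frequency cuts.

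| Levels | Unweighted kappa, ICC 0.90 | Quadratic-weighted kappa, ICC 0.90 | Unweighted kappa, ICC 0.80 |
|---|---|---|---|
| 2 | 0.71 | 0.71 | 0.59 |
| 3 | 0.61-0.64 | 0.75-0.80 | 0.47-0.49 |
| 5 | 0.46-0.53 | 0.83-0.85 | 0.33-0.37 |
| 10 | 0.29-0.32 | 0.88 | 0.19-0.20 |
| 25 | 0.13-0.14 | 0.89-0.90 | 0.08-0.09 |

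With equal-width cuts, the absolute-agreement ICC of the categorised ratings equals the quadratic-weighted kappa to the digits shown. As levels are added, the weighted measure rises towards the true value while unweighted kappa falls towards zero.

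**At the trial's size.** With 54 rated videos, 9 equal-width levels and a true ICC of 0.90, the central 95% of sample values is 0.18-0.51 for unweighted kappa and 0.80-0.93 for the ICC.

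**Limiting case.** Two raters who always differ by exactly one point on a 0-32 score give unweighted kappa −0.03, quadratic-weighted kappa 0.99 and ICC 0.99.

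**The case against.** The strongest reply is that the plan does not say it will do the poor thing. Weighted kappa is also Cohen's kappa, and with quadratic weights it tracks the ICC. Kappa may be meant for single items, and item-level kappa beside a summed score used in correlations is a coherent plan. A yes/no checklist is plausible while the instrument is still being developed, and unweighted kappa would suit its items. All of this stands. It means that a reader may not conclude that a numeric total will definitely be judged by unweighted kappa. It does not settle the matter, because neither the weights nor the unit is stated, and the item-level reading leaves the reliability of the analysed score unreported.

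A second reply concerns the mixed models. The sentence on change does not say whether proficiency is the response or a covariate, and the models it refers to are described for efficacy outcomes. That also stands. The reading of proficiency as a quantity rests mainly on the Pearson sentence, with the change analysis as support.

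A third reply is that nothing in the plan turns on the value. The feasibility criteria in 1.2 and 19.1 concern recruitment, retention, attendance and adherence; no reliability threshold is set. This stands too. A reader might infer that the instrument would fail a test, or that the Pearson or mixed-model estimates would be wrong. The documents support neither: the choice of kappa does not alter the scores or those estimates. Nor does the plan say that it needs a measurement-error variance for change scores.

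**Conclusion.** The point holds as a mismatch between the reliability statistic and the score analysed, left open by missing specification. Either kappa is applied unweighted to the score, and reliability is understated, or it is applied to items, and the reliability of the score used for primary objective 2 is not reported. Only a weighted kappa on the score itself would escape both, and the plan does not state one.

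The size is conditional. At a true ICC of 0.90 the understatement is nil at 2 levels, modest at 3 (about 0.11 to 0.18 below quadratic-weighted kappa) and large from 5 levels upwards (about 0.30 to 0.39 at 5, and about 0.75 at 25). These figures assume two unbiased raters and normal true scores.

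It would go too far to say that kappa will make this instrument look unreliable: that needs a scale and a benchmark, and the documents give neither. Confidence is moderate for that reason. The change is still worth making, because it is cheap and a primary objective uses the instrument.

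**What to change.** Amend the reliability sentence in 19.1 before any videos are rated:

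- State the score range, the item format, the number of raters and the number of videos to be rated.
- For the proficiency score used in the Pearson and mixed-model analyses, report an absolute-agreement ICC with 95% confidence interval. Match its form to the rater design: two-way random-effects, single-rater if the result is to generalise to other raters and single ratings are analysed; another form if the raters are fixed or ratings are averaged.
- For ordinal items, report quadratic-weighted kappa. Keep unweighted kappa for yes/no or nominal items.

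The cost is a sentence or two of text. The same ratings serve, and no further data or participants are needed. Naming the weights in advance also removes a choice that could otherwise be made after seeing the results.
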